2.4.1 Microbiome Preliminary Data

In collaboration with [name]. at the University of Pennsylvania and postdoctoral fellow, [name]., we sequenced 16S rRNA bacterial sequences from the skin of the first 12 (five with active ulcers) study participants using the Illumina MiSeg Technology. Approximately 1.3 million sequences were taxonomically classified using the online molecular ecology tool, mothur, and the RDP classifier and training set (version 9).

The relative abundance of bacteria on the ankles of SCD participants with and without legulcers is distinct. Those with leg ulcers have lower bacterial diversity and an abundance of the skin commensal, Staphylococcus, while those without leg ulcers display higher bacterial diversity. This finding supports the claim that microbial diversity is higher in a healthy state and is. conversely, lower in a disease state. Additionally, we conducted Principle Coordinate Analysis (PCoA) using thetayc distances comparing bacterial community structure (similarity) in participants with and without leg ulcers. This analysis confirmed that the two communities differ. and we speculate that this variation could potentially explain the differences in the skin microbiome of individuals with SCD who develop leg ulcers over their life course. We are currently processing microbiome samples as they are collected and will complete the sequence analysis when the data is available.

[figure not shown]

Figure 4 Legend: Approximately 1.3 million 16S rRNA bacterial sequences were taxonomically classified using the online molecular ecology tool, mothur, and the RDP classifier and training set (version 9). Participants #0002, 0003, and 0005 are shown. Swab samples were collected from an ulcer and the contralateral leg without an ulcer, and samples were sequenced.

During the abovementioned phase 1 trial of topical sodium nitrite, we observed no SAE's. We documented a grade 1 decrease in diastolic blood pressure below 50 mmHg, judged as possibly related to study drug 16 times in 4 participants. Of the four participants, two enrolled in Cohort 4, the highest concentration of the drug (2.0% sodium nitrite cream) and the other two enrolled into Cohort 3.a (1.8% sodium nitrite cream). The participants had fluctuating diastolic blood pressure measurements that occasionally reached below 50 mmHg even **before study cream application**; therefore, the association with study cream application is unclear. All events resolved spontaneously within an hour (i.e., at the next BP check).

15

PI: [name] Version 5

Experiments in rats showed that methemoglobin levels peaked at 45-50 min after application of 30 g/L sodium nitrite solutions on abraded skin³². Percutaneous absorption of a solution differs from the absorption rate from Aquaphor (the vehicle in our current preparation) and it seems to be slower than that from solution. There was no evidence of accumulation either, as predicted by our pharmacokinetic models^{34,35}.

In the proposed phase 2 trial we plan to answer this toxicity question, since we will be treating patients blindly with a placebo preparation and we will be able to ascertain whether the fluctuations in BP are intrinsic to this patient population, their frequent use of opioids, and/or chronic wide pulse pressure.

3.0 Specific Aims

Hypotheses:

- •Topical sodium nitrite cream, at 2% concentration, is safe and well tolerated when applied for an extended period of time (10 weeks) in patients with sickle cell disease and leg ulcers.
- •Topical sodium nitrite accelerates healing of skin ulcers and decreases ulcer relatedpain compared to placebo in patients with sickle cell disease and leg ulcers.

Specific Aims:

- To determine the safety and tolerability of prolonged (10 weeks), twice a week application of topical sodium nitrite in patients with sickle cell disease and leg ulcers
- To determine if topical sodium nitrite accelerates wound healing as defined by >25% improvement over placebo arm
- •To determine if topical sodium nitrite decreases pain at the wound site >20% over placebo

Secondary Objectives:

- To evaluate the effect of hydroxyurea on leg ulcer's healing in combination with topical sodium nitrite or placebo
- To assess changes in ulcer microbiome after application of sodium nitriteor placebo and how they may relate to rate of healing
- •To evaluate the dermal composition and microvascular structure in the ulcer's biopsy of subjects enrolled on this study.

4.1 Inclusion and Exclusion Criteria

4.2 Eligibility

Subjects must be at least 18 years of age and have provided informed, written consent for participation in this study.

Each subject must meet all of the following inclusion criteria during the screening process in order to participate in the study:

- Subjects must have a diagnosis of sickle cell disease (SS, SC, Sß-thalassemia, SD, SOArab).
- Have one or more ulcers in one or both legs and/orfeet.

- •Leg ulcers that will receive treatment must be no larger than 100 cm².
- •No history of congenital methemoglobinemia.
- •Have documented normal G6PD activity.

4.3 Exclusion Criteria

Subjects meeting any of the following criteria during baseline evaluation will be excluded from entry into the study:

- •Exposure to therapeutic nitric oxide, L-arginine, nitroprusside, or nitroglycerine within the past 1 week.
- Subjects presenting with clinically-diagnosed bacterial infection (e.g., osteomyelitis, pneumonia, sepsis, or meningitis).
- •Subjects who have a pre-existing methemoglobinemia (more than 3.5% on two different occasions).
- •Patients who are currently enrolled in any other investigational drug study (this does not include observational or natural historyprotocols).
- •Use of PDE5 inhibitors, such as sildenafil, 4 days prior to screening.
- •Pregnant women (urine or serum HCG +) or nursing mothers.
- The following list of drugs and agents may cause methemoglobinemia and should be avoided while on this study:

Anesthetics (local): Benzocaine, procaine, prilocaine, Anbesol, Orajel

Antimalarials: chloroquine, primaquine, quinacrine

Aniline dyes

Chlorates

Dapsone

Diarylsulfonylureas

Doxorubicin

Metoclopramide

Nitric and nitrous oxide

Nitrobenzenes (shoe and floor polish and in paint solvents)

Nitroethane (artificial nail remover, propellant, fuel additive)

Nitrofurantoin (furadantin)

Pyridium (phenazopyridine)

Phenacetin

Phenylhydrazine

Rasburicase

Sulfonamides (sulfacetamide, sulfamethoxazole, sulfanilamide, sulfapyridine)

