5.1 Study Design and Methods

5.2 Overview

This will be randomized, placebo controlled, double blinded study

We plan to enroll fifty subjects with homozygous sickle cell disease (HbSS), sickle-thalassemia (Hb S-ß thalassemia), HbSC, HbSD, or HbSO^{Arab}, in order to have 40 subjects complete at least 8 weeks of treatment, after an expected 20% dropout.

Subjects will receive 2% topical sodium nitrite cream twice a week for 10 weeks or placebo with vehicle only.

Subjects will have 0.1 cm of 2% sodium nitrite cream or placebo cream applied per 1 cm² of the total ulcerated area. If a subject has more than one ulcer, all of them will be treated with either "study cream" or placebo. Areas will be rounded to the nearest 1 cm². If a subject has more than one ulcer and the total sum of all of them is above 100 cm², then one of the ulcers can be enrolled

PI: [name]

^{*} If a patient does not qualify because he/she has an infection at the time of enrollment or at run-in, he/she can initiate the protocol two weeks after the infection has been cleared.

in the study, as long as it does not exceed the 100 cm² size. The other wounds will continue standard of care only. The total amount of sodium nitrite administered to each subject will vary depending upon the size of the ulcer but the treated total surface area will not exceed 100 cm² (i.e., subjects will receive a maximum of 10 cm of sodium nitrite cream).

Administration of study cream or placebo will be double blinded. The pharmacist will not be blinded, so he/she will be aware of who is receiving the investigational drug for safety purposes.

Randomization:

Randomization will be stratified by use of hydroxyurea to minimize its potential confounding effect on the study outcomes; we expect that 50% of participants use hydroxyurea. In addition, within each stratum (use or non-use), random treatment assignment will be balanced, i.e., 1:1 allocation, within blocks. This type of stratified block-randomized allocations will be generated by the study statistician applying a computer algorithm. The randomized allocation will occur once a subject is determined to be eligible for participation after the screening visit and the run in phase, but prior to the first cream application.

Un-blinding Procedures:

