The medical monitor may request unblinding to attribute toxicities if a serious adverse event occurs to determine attribution, or if a dose limiting toxicity occurs to determine if placebo or active treatment was used.

A run in period of at least 2 weeks will be conducted, during which patients will receive/optimize wound care at the Center that will enroll the subjects, following standard of care, routinely available therapies. Patients that experience a reduction of their wound size by >25% during this time will be excluded from the trial, as this suggests an effect secondary to improved wound care only. These patients will remain on protocol and their wound will be measured monthly for up to 6 months or until closure, whichever comes first. If a subject develops an acute vaso-occlusive episode and is hospitalized during the run in period, he/she will have the run in period extended in order to allow the subject to be safely discharged from the hospital and return to outpatient care.

Close monitoring of VSS, especially BP, will be done, to assess changes in patients receiving study cream, compared to placebo.

Measurements of all leg ulcers and photographs will be obtained at the following points: At Baseline

After the 2 weeks run in period, to determine eligibility for study cream application
At mid-point: after 10 applications of study cream, to determine the need for drug modification
At end of study: after the last application of the study cream

An accurate assessment of pain will be obtained each time that size measurements are obtained.

Quality of life questionnaire (ASCQ-Me) will be given before initial application and at the end of protocol or when the ulcer(s) is (are) healed, whatever comes first.

We will monitor metHb level as a safety measure, despite the fact that the phase 1 study did not show significant elevations of metHb. **Teratogenicity** is not a consideration, since the phase 1 study demonstrated minimal systemic absorption of nitrite and nitrate, therefore the risk for the gonads and potential offspring is limited to nonexistent.

Among the entry studies to be obtained, a **3-4 mm skin optional biopsy** may be performed at the edge of the ulcerated area. If the patient has multiple ulcers, the surgeon/wound care expert will decide which one is the safest to biopsy. This will be done

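### PDE5 inhibitors, L-arginine, nitroprusside and nitroglycerine are barred before entry, but no rule restricts them during the 10 weeks of cream

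*Combined protocol and SAP*

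**What the plan says.** Section 4.3 opens with "Subjects meeting any of the following criteria during baseline evaluation will be excluded from entry into the study". Two of the criteria that follow concern vasoactive drugs: "Exposure to therapeutic nitric oxide, L-arginine, nitroprusside, or nitroglycerine within the past 1 week" and "Use of PDE5 inhibitors, such as sildenafil, 4 days prior to screening". The first gives no reference date for its window; the second is dated from screening.

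The same section has one list that applies during the trial: "The following list of drugs and agents may cause methemoglobinemia and should be avoided while on this study". It includes "Nitric and nitrous oxide", but not PDE5 inhibitors, L-arginine, nitroprusside or nitroglycerine.

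First cream does not follow entry directly. Section 5.2 says "A run in period of at least 2 weeks will be conducted", and allows allocation only for someone who has been "determined to be eligible for participation after the screening visit and the run in phase, but prior to the first cream application". Sections 5.2 and 5.3 state one test at the end of run-in: whether ulcer area has fallen by more than 25%.

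The schedule of procedures records concomitant medications at screening, at baseline, twice a week from Visit 3 and at End of Study. The run-in column is blank. No text says what to do if one of the four drugs appears in that record.

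**The concern.** The protocol treats recent use of these drugs as a reason to keep a subject out, then does not mention them once cream is on the wound. An entry washout protects the treatment period only if the drug stays away.

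Section 4.3 gives no reason for the exclusions. The likely one is additive vasodilation, which is an inference, though the protocol gives it some footing: section 10 lists vasodilatation among the cream's toxicities, and Table 2 in section 12 lists peripheral vasodilation with hypotension as an expected event possibly related to study drug.

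Two things are at stake. The first is avoidable hypotension risk, including at home doses. The second is interpretation. Section 8.1 makes tolerability and adverse effects the primary endpoint, and section 2.4.2 says the placebo comparison will settle whether the blood-pressure fluctuations seen in phase 1 belong to this population. A co-administered vasodilator makes an individual event harder to assign.

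**Working it through.** The plan states no figure on this point to reproduce. The check compares the rules across sections and does a little arithmetic.

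**Step 1. Entry rule against on-study rule (section 4.3).**

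| Agent or class | Barred at entry | On the on-study avoid list |
|---|---|---|
| Therapeutic nitric oxide | yes, past week | yes |
| L-arginine | yes, past week | no |
| Nitroprusside | yes, past week | no |
| Nitroglycerine | yes, past week | no |
| PDE5 inhibitors | yes, 4 days before screening | no |

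Five are barred at entry and one carries over: 5 − 1 = 4 without an on-study rule. The run-in and visit text (5.2, 5.3), dose adjustment (5.4), stopping rules (7.2) and schedule add none.

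**Step 2. Are the washouts themselves too short?** With a run-in of at least 14 days, a subject who does not restart has been off drug at first cream for at least:
- PDE5 inhibitors: 4 + 14 = 18 days
- the other three: 7 + 14 = 21 days

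The washouts are adequate on their own terms. The gap is use started or resumed afterwards.

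**Step 3. The period without a rule.** Planned treatment is 10 × 7 = 70 days, plus the interval to End of Study, because section 5.3 has the cream removed the week after the last application. Subjects who heal or drop out have less. In the run-in, the PDE5 window is anchored to screening and no text re-applies it. The one-week window could be re-applied at the eligibility decision after run-in, but no text says so.

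**Step 4. Blood-pressure checks around doses (section 5.3).** Applications: 10 × 2 = 20, at Visits 3 to 22. Post-application pressure is taken at Visit 3 and at Visits 4 to 6. If it is stable at Visits 4 to 6, it is no longer needed. That leaves at most 20 − 4 = 16 applications (Visits 7 to 22, weeks 3 to 10) with no required post-application reading. Eight of the 16 are second weekly doses, which may be given at home, where no pressure check is described. Sixteen is an upper bound, because section 7.1 states checks at hours 1 to 5 without naming a visit.

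**Step 5. Attribution (section 12.2, Table 4).** Possibly, probably and definitely related all require that the event is not readily produced by other interventions. A pressure fall shortly after cream in a subject taking a PDE5 inhibitor would fail that condition. It would not fit the probably-not-related category either, which requires no temporal association with study product. Such an event has no clear place in the scale.

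**The case against.** The strongest reply is that the feared harm is inferred and the protocol already guards against it.

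- **Phase 1 is reassuring.** Diastolic pressure fell below 50 mmHg in 2 of 3 subjects at the 2% dose, but these events were grade 1, resolved within an hour, and occurred in participants whose diastolic pressure sometimes dropped that low before cream. Mean arterial pressure did not change, pressure changes did not correlate with nitrite levels, and systemic absorption was minimal.
- **Hypotension is managed whatever its cause.** It is a dose-limiting toxicity (5.4) and a ground for removal (7.2). A dose is skipped at a systolic pressure of 80 mmHg or below and/or a diastolic of 50 mmHg or below, with removal after three skips in a row. Vital signs are taken on arrival. Home dosing is offered only if early subjects show no significant side effects, and a home health nurse may give it.
- **Use is visible.** On-treatment medications are recorded, and section 7.2 lets the investigator stop treatment.

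Most of this stands and keeps the point small. It does not close the gap: the rules act on low pressure once it occurs, not on the drug that may have caused it, and recording a drug is not a rule about it.

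A reader might infer that these drugs are wholly unrestricted through run-in and treatment, for at least 12 weeks. The documents do not support that. The one-week window may be re-applied after run-in, the run-in days carry no cream, and treatment can end early through healing or dropout, so 12 weeks is not a minimum.

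**Conclusion.** The concern holds as a cheap improvement. Four agents or classes barred before entry have no on-study rule during the planned 10 weeks of cream and the interval to End of Study. For PDE5 inhibitors the run-in is uncovered too; for the other three, coverage of the run-in is ambiguous.

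The size is modest and cannot be put as a number of subjects, because the documents give no rate of use. The conclusion rests on two assumptions: that the exclusions were meant to prevent additive vasodilation, and that some subjects would start or resume one of these drugs.

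A reader might also infer that the arm comparison is biased. That is not supported: under blinded randomisation, use should be balanced in expectation. In addition, the primary test in section 8.1.1 compares numbers of adverse events, without conditioning on attribution. What suffers is subject safety at the margin and the reading of individual blood-pressure events.

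**What to change.** Keep the existing washouts and make three additions.

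1. **Avoid list.** Add PDE5 inhibitors, L-arginine, nitroprusside and nitroglycerine to the drugs to be avoided on study in section 4.3, through the End of Study visit (Visit 23).
2. **Check at Visit 3.** Before allocation, confirm from the medication record already scheduled there that the subject has had no PDE5 inhibitor in the past 4 days and none of the other three in the past week. If not, delay allocation and first application until the window is clear.
3. **Necessary use.** If one of these drugs becomes clinically necessary, give it, record it, decide on continuing cream under the discretion rule in section 7.2, and flag the use in the safety analysis.

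The cost is a wording amendment and one short check at an existing visit. A few subjects may be delayed by up to 4 to 7 days, and an occasional one lost, which is a real price in a trial of 50. The delay fits the design: the run-in has no stated maximum, and for a subject hospitalised with a vaso-occlusive episode section 5.2 already says "he/she will have the run in period extended".

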5.1 Study Design and Methods

5.2 Overview

This will be randomized, placebo controlled, double blinded study

We plan to enroll fifty subjects with homozygous sickle cell disease (HbSS), sickle-thalassemia (Hb S-ß thalassemia), HbSC, HbSD, or HbSO^{Arab}, in order to have 40 subjects complete at least 8 weeks of treatment, after an expected 20% dropout.

Subjects will receive 2% topical sodium nitrite cream twice a week for 10 weeks or placebo with vehicle only.

Subjects will have 0.1 cm of 2% sodium nitrite cream or placebo cream applied per 1 cm² of the total ulcerated area. If a subject has more than one ulcer, all of them will be treated with either "study cream" or placebo. Areas will be rounded to the nearest 1 cm². If a subject has more than one ulcer and the total sum of all of them is above 100 cm², then one of the ulcers can be enrolled

PI: [name]

^{*} If a patient does not qualify because he/she has an infection at the time of enrollment or at run-in, he/she can initiate the protocol two weeks after the infection has been cleared.

in the study, as long as it does not exceed the 100 cm² size. The other wounds will continue standard of care only. The total amount of sodium nitrite administered to each subject will vary depending upon the size of the ulcer but the treated total surface area will not exceed 100 cm² (i.e., subjects will receive a maximum of 10 cm of sodium nitrite cream).

Administration of study cream or placebo will be double blinded. The pharmacist will not be blinded, so he/she will be aware of who is receiving the investigational drug for safety purposes.

Randomization:

Randomization will be stratified by use of hydroxyurea to minimize its potential confounding effect on the study outcomes; we expect that 50% of participants use hydroxyurea. In addition, within each stratum (use or non-use), random treatment assignment will be balanced, i.e., 1:1 allocation, within blocks. This type of stratified block-randomized allocations will be generated by the study statistician applying a computer algorithm. The randomized allocation will occur once a subject is determined to be eligible for participation after the screening visit and the run in phase, but prior to the first cream application.

Un-blinding Procedures:

The medical monitor may request unblinding to attribute toxicities if a serious adverse event occurs to determine attribution, or if a dose limiting toxicity occurs to determine if placebo or active treatment was used.

A run in period of at least 2 weeks will be conducted, during which patients will receive/optimize wound care at the Center that will enroll the subjects, following standard of care, routinely available therapies. Patients that experience a reduction of their wound size by >25% during this time will be excluded from the trial, as this suggests an effect secondary to improved wound care only. These patients will remain on protocol and their wound will be measured monthly for up to 6 months or until closure, whichever comes first. If a subject develops an acute vaso-occlusive episode and is hospitalized during the run in period, he/she will have the run in period extended in order to allow the subject to be safely discharged from the hospital and return to outpatient care.

Close monitoring of VSS, especially BP, will be done, to assess changes in patients receiving study cream, compared to placebo.

Measurements of all leg ulcers and photographs will be obtained at the following points: At Baseline

After the 2 weeks run in period, to determine eligibility for study cream application
At mid-point: after 10 applications of study cream, to determine the need for drug modification
At end of study: after the last application of the study cream

An accurate assessment of pain will be obtained each time that size measurements are obtained.

Quality of life questionnaire (ASCQ-Me) will be given before initial application and at the end of protocol or when the ulcer(s) is (are) healed, whatever comes first.

We will monitor metHb level as a safety measure, despite the fact that the phase 1 study did not show significant elevations of metHb. **Teratogenicity** is not a consideration, since the phase 1 study demonstrated minimal systemic absorption of nitrite and nitrate, therefore the risk for the gonads and potential offspring is limited to nonexistent.

Among the entry studies to be obtained, a **3-4 mm skin optional biopsy** may be performed at the edge of the ulcerated area. If the patient has multiple ulcers, the surgeon/wound care expert will decide which one is the safest to biopsy. This will be done

PI: [name] Version 5 in order to assess cutaneous vascularization (i.e., angiogenesis), inflammation (tissue II-6, TGF- \Box , etc.), and markers of neurogenic inflammation³⁶.

At the end of 10 weeks of treatment, subjects that still have an open ulcer will be offered continuation of care at Montefiore or University of Pittsburg or referred back to the community.

Subjects will be followed off treatment but on study with monthly visits for an additional six months to evaluate the long term effect of topical sodium nitrite on the host and the ulcer (how many ulcers re-open or close). These visits will consist of measurement of all wounds by light photography and a detailed history of intervening ulcer treatments. If patients cannot return to the hospital or have moved away, we will call them and obtain the information on the phone and ask for a photograph. The photo can be obtained by the patient him or herself. Thereafter, they will be followed up with phone calls once a year for a total of 2 years, to establish whether this therapy is changing the natural history of ulcers in this population.

Rationale for the selection of subjects' number and endpoints

Sample size: We plan to randomize a total of 50 subjects to sample size of 20 completers per arm (40 subjects total) after an anticipated 20% dropout rate is taken into account. This sample size is determined based on feasibility of recruitment within the budget constraint and time frame of the study; we anticipate enrolling 1~2 eligible subjects per month. Although the focus of analysis will be more on estimation of treatment effect sizes and their 95% confidence intervals, the anticipated sample size is adequate to detect 88% vs. 48% response rate, as defined by >25% reduction of ulcer size from baseline, between treatment and control groups, with >80% at a two-sided significance level of 0.05 (see table 1). We note that in the Phase 1 study we observed an 88% response rate. Therefore, our study will be adequately powered if response rate in the placebo group is smaller than 48%.

Rationale for end point of decrease in ulcer size: A decrease of 25% from baseline was used as a significant end point in Perrine's study of arginine butyrate in SCD leg ulcers³⁷. The FDA's own guidelines for research in cutaneous ulcers and burns specify: "Measurement of partial wound healing in early phase clinical trials, if prospectively defined, may indicate relevant biological activity and help guide subsequent trial design". Therefore, since this is a phase II trial, I think it is prudent to be conservative and reserve the complete closure end point for the phase III trial. Recently [name] and other dermatologists have challenged the idea of complete closure as the only end point for skin ulceration as being counterproductive for the development of new therapies, and significantly different from standards used in cancer trials, where a 10-20% response rate is often sufficient to claim success of a drug ordevice³⁸.

Pain threshold: A decrease of 20% was selected based on the accepted change of pain of **minimum 2 point** decrease on the VAS scale being considered as significant in clinical end point in research settings³⁹. The VAS scale ranges from 0-10, so 20% change is 2 points. Moreover, the finding of improvement in pain at the treated ulcer site was very interesting and needs further investigation.

In the phase 1 study⁴⁰ we conducted, we observed an increase in blood flow in the skin of individuals with chronic ulceration compared to an area that was not ulcerated. The lack of controls without ulcers prevented us from concluding that the high blood flow had a causative effect on the ulcer formation and delayed healing. Furthermore, it was not clear whether the high blood flow observed at baseline, i.e., before cream application, was different than what we would expect in patients with SCD.

Secondary end points were chosen in order to further our knowledge of the etiology of poor healing in SCD ulcers, based on the results from the prior study.

19

PI: [name] Version 5

Rationale for the study of changes in microbiome. One of the most studied effects of NO is its bactericidal and general antimicrobial activity. NO exhibits nitrosative and oxidative action alone and after reacting with oxygen, such as peroxy-nitrite, RSNOs, and nitrogen dioxide⁴¹. These species affect microbial proteins, DNA, and metabolic enzymes, disrupting cellular walls and functions. NO acts on both planktonic bacteria and biofilm communities⁴². It is likely that a significant portion of the wound healing properties of NO are mediated through its bactericidal properties, through a reduction in biofilm and inflammation. We propose to examine changes in the microbiome.

Rationale for the sodium nitrite dose: The completed phase I, dose-escalating study identified the 2% concentration as the most effective for wound healing. Two of the three subjects in this cohort experienced complete closure, for a healing rate of 86%, higher than any of the other cream concentrations. The maximum sodium nitrite dose that will be administered to patients at this dose level is 55 mg per dose. This amount of sodium nitrite is 18% of the total sodium nitrite dose that is approved by the FDA for use in the emergency treatment of cyanide poisoning (i.e. 300 mg), and is predicted to produce a peak whole blood sodium nitrite concentration of approximately 29 µmol/L if given as an intravenous bolus or 5 µmol/L if infused over 15 minutes. These levels of systemic nitrite should be safe, as similar nitrite concentrations were observed and well tolerated in one of our healthy volunteer studies (05-H-0088). A median (range) nitrite peak concentration of 20 µmol/L and a steady state level of 8 (4 – 12) µmol/L were attained during the phase I study, significantly lower than what was previously reported to be safe. This indicates that sodium nitrite is minimally absorbed when applied topically, even on abraded skin. Methemoglobin reached 4.1% at its highest level in one subject, while did not change from baseline in any of the other 17 subjects. Mean arterial blood pressure did not change, while diastolic blood pressure decreased below a predetermined threshold of 50 mmHg in 2/3 subjects at this dose level. There was no correlation between nitrite and nitrate levels and changes in BP.

